### 9.3.4. Derived Variables

All variables to be used in the final study analyses including those that are derived from curated and extracted data, will be formally defined in the SAP. Variables derived from abstracted and extracted data will include the following:

- Age at index date.
- BMI at index date ( $\pm 30$  days).

- Geographic census region of residence.
- Weighted index of comorbid disease condition. Weighting of comorbid conditions will follow the weighting as specified in the Charlson Comorbidity Index.
- Start and end dates and start and end dose of infused anti-cancer treatments from the index date through the end of the third R/R-based line of therapy or the end of the record, whichever occurs first.
- Dose changes of all oral (if applicable), infused, or injected anti-cancer therapies from the index date through the end of the third R/R-based line of therapy or the end of the record, whichever occurs first.
- Start and end schedule of infused anti-cancer treatments from the index date through the end of the third R/R-based line of therapy or the end of the record, whichever occurs first.
- Treatment regimens, derived from oral and infused agents delivered, including start and stop dates.
- Duration of anti-cancer treatments regimens from the index date through the end of the third R/R-based line of therapy or the end of the record, whichever occurs first. Duration will be calculated as the end date of last agent within a regimen minus the start date of the corresponding regimen and will be computed during the analytics phase of the project.
- Time under observation for analysis of EFS/RFS, by line, based on start date of treatment within line and dates of R/R event or disease progression, or censoring.
- Time under observation for analysis of OS from start of the first qualifying Mylotarg-containing R/R-based line of therapy, based on start of treatment in the first qualifying line setting, and based on date of death or censoring.
- Time to best response for the first qualifying Mylotarg-containing R/R-based line of therapy from the index date through the end of the third R/R-based line of therapy or the end of the record, whichever occurs first.
- Duration of tumor response for the first qualifying Mylotarg-containing R/R-based line of therapy from the index date through the end of the third R/R-based line of therapy or the end of the record, whichever occurs first.

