### 9.7.2. Time to Event Analysis

Single time to event analyses will be conducted as specified under the study objectives.

CCI

Real world time to event outcomes in this study will include:

- rwEFS/rwRFS for each of the first three R/R-based lines of therapy. rwEFS will be defined as the time from the treatment initiation date (for the first line of therapy) to the date of treatment failure (TF), relapse from Complete Response (CR) or better, or death from any cause, whichever comes first. TF is defined as failure to achieve CR or better following up to 6 cycles of Mylotarg. rwRFS will be defined as the time from the treatment initiation date (for the first line of therapy) to the date of a relapse event, or death from any cause, whichever comes first.
- rwOS, from the first line of therapy through the end of record or death, whichever occurs first, and
- Duration of therapy across lines of therapy from the first line of therapy through the third R/R-based line of therapy.

The time origin for analysis of rwEFS/rwRFS is the start of therapy within each specific line of therapy, and the terminal event is the earlier of an R/R event or death. The time origin for analysis of rwOS is the start of therapy within the first line of therapy, and the terminal event is death. The time origin for analysis of duration of therapy is start of Mylotarg, and the terminal event is discontinuation of that therapy.

### 9.7.3. Methods Under Objective 1

*Objective 1: To describe the demographic and clinical characteristics as outlined in the variable list below for patients diagnosed with AML who received Mylotarg in a real-world setting.*

Descriptive analysis as detailed in [Section 9.7.1](#) will be conducted for work under this objective. Demographic characteristics that will be reported will include the distribution of sex, patient age, race/ethnicity, height, weight, BMI, insurance status, and region of residence closest to the index date. Clinical characteristics that will be reported will include the distribution of comorbidity status and comorbidity index score, ECOG score, and disease characteristics, such as stage at index date, cytogenetic testing at index date, and whether the AML diagnosis was de novo versus secondary.

Demographic and clinical characteristics will not be stratified by a primary grouping variable.

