#### **9.7.5. Methods Under Objective 3**

*Objective 3: To describe the effectiveness outcomes of treatment of AML patients who received Mylotarg in a real-world setting.*

Analysis under this objective will include all study patients. The outcomes of interest under this objective are rwEFS/rwRFS and real world overall survival. Time to event analysis as described in [Section 9.7.2](#) will be utilized.

The Kaplan-Meier product limit estimator will be employed to evaluate rwEFS/rwRFS and rwOS. The time origin for these analyses will be the start of the treatment in the respective line of therapy for rwEFS/rwRFS for the first 3 R/R-based lines of therapy. The time origin of rwOS analysis is the start of the earliest line of Mylotarg therapy. rwEFS/RFS and rwOS analyses for lines of therapy will be limited to patients who received treatment during the line of interest.

The terminal event for analysis of rwEFS/rwRFS is the earlier of death or the first date of disease progression or R/R event following the time origin. Patients who have not died or experienced a disease progression or R/R event by the end of the medical record will be censored for analysis of rwEFS/rwRFS. The terminal event for analysis of rwOS is date of death. Note that Social Security Disability Insurance (SSDI) records have an expected lag of up to 4 months. Accordingly, patients who are not indicated to be deceased in clinical records or SSDI records will be censored for rwOS analysis as of the later of 1) the latest date known alive within the clinical record, 2) 4 months prior to the date of most recent SSDI update.

Separate Kaplan-Meier analyses will be conducted for each rwEFS/rwRFS and rwOS endpoint.

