### 3.5.2. Derived Variables

Variables derived from abstracted and extracted data will include the following:

- Age at index date (Table 1).
- BMI at index date ( $\pm 30$  days) (Table 1).
- Geographic census region of patient's residence (Table 1).
- Weighted index of comorbid disease condition. Weighting of comorbid conditions will follow the weighting as specified in the Charlson Comorbidity Index (Table 2).
- Start and end dates and start and end dose of infused anti-cancer treatments from the index date through the end of the third R/R-based line of therapy or the end of the record, whichever occurs first.
- Dose changes of all oral (if applicable), infused, or injected anti-cancer therapies from the index date through the end of the first R/R-based line of therapy or the end of the record, whichever occurs first (Table 4).
- Start and end schedule of infused anti-cancer treatments from the index date through the end of the third R/R-based line of therapy or the end of the record, whichever occurs first (Table 3-Table 5).
- Treatment regimens, derived from oral and infused agents delivered, including start and stop dates, and indication of subsequent treatment after 1L (Table 3-Table 5).
- Duration of anti-cancer treatments regimens from the index date through the end of the third R/R-based line of therapy or the end of the record, whichever occurs first. Duration will be calculated as the end date of a regimen minus the start date of the corresponding regimen and will be computed during the analytics phase of the project (Table 5).
- Time under observation for analysis of rwEFS/rwRFS, by line, based on start date of treatment within line and dates of R/R event or disease progression, or censoring (Table 5-Table 7).
- Time under observation for analysis of rwOS from start of the first qualifying Mylotarg-containing R/R-based line of therapy, based on start of treatment in the first qualifying line setting, and based on date of death or censoring (Table 8).

- Time to best response for each regimen in the first qualifying Mylotarg-containing R/R-based line of therapy from the index date through the end of the third R/R-based line of therapy or the end of the record, whichever occurs first (Table 9-Table 11, Table 14-Table 15).

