#### 4.3.2. Time to Event Analysis

Single time to event analyses will be conducted as specified under the study objectives. CCI [REDACTED]

Real-world time to event outcomes in this study will include:

- rwEFS/rwRFS for the first 3 R/R-based lines of therapy. rwEFS will be defined as the time from the treatment initiation date (for the first agent in the first regimen in the first line of Mylotarg-containing therapy) to the date of treatment failure (TF), relapse from Complete Response (CR) or better, or death from any cause, whichever comes first. TF is defined as failure to achieve CR or better following up to 3 cycles of Mylotarg. rwRFS will be defined as the time from the treatment initiation date (for the first agent in the first regimen in the first line of therapy) to the date of a relapse event, or death from any cause, whichever comes first.
- rwOS, from the first line of therapy through the end of record or death, whichever occurs first, and
- Duration of therapy across lines of therapy from the first line of therapy through the third R/R-based line of therapy.

The time origin for analysis of rwEFS/rwRFS is the start of therapy within each specific line of therapy, and the terminal event is the earlier of an R/R event or death. The time origin for analysis of rwOS is the start of therapy within the first line of therapy, and the terminal event is death. Patients who are not indicated to be deceased at last known contact (patients who are alive, or lost to follow-up) will be censored. The time origin for analysis of duration of therapy is start of Mylotarg, and the terminal event is discontinuation of that therapy.

#### 4.3.3. Methods under Objective 1

*Objective 1: To describe the demographic and clinical characteristics as outlined in the variable list below for patients diagnosed with AML who received Mylotarg in a real-world setting.*

Descriptive analysis as detailed in [Section 4.3.1](#) will be conducted for work under this objective. Demographic characteristics that will be reported will include sex, patient age, race/ethnicity, height, weight, BMI, insurance status, and region of residence closest to the index date. Clinical characteristics that will be reported will include comorbidities and comorbidity index score, ECOG score, and disease characteristics, such as stage at index date, cytogenetic testing at index date, and whether the AML diagnosis was de novo versus secondary.

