Demographic and clinical characteristics will not be stratified by a primary grouping variable.

#### 4.3.4. Methods under Objective 2

*Objective 2: To describe the treatment patterns from the diagnosis of AML through the end of the third R/R-based line of therapy.*

Analysis under this objective will include all study patients. Descriptive analysis as detailed in [Section 4.3.1](#) will be conducted for work under this objective. Treatment patterns include description of regimens within line of therapy for the first 3 R/R-based lines of systemic therapy as well as the description of sequences of regimens across the first 3 R/R-based lines of systemic therapy. Description of treatment regimens within line includes the frequency and percentage of each agent/regimen received, by regimen in sequence, by line, for the first 3 R/R-based lines of systemic therapy. In addition, the analysis will descriptively characterize the starting dose and dose changes of Mylotarg in each of the first lines of therapy.

Duration of treatment will also be descriptively analyzed across lines of therapy, starting with the first agent or regimen in the first line of therapy for the first 3 R/R-based lines of therapy.

### 4.3.5. Methods under Objective 3

*Objective 3: To describe the effectiveness outcomes of treatment of AML patients who received Mylotarg in a real-world setting*

Analysis under this objective will include all study patients. The outcomes of interest under this objective are rwEFS/rwRFS and rwOS. Time to event analysis as described in [Section 4.3.2](#) will be utilized.

The Kaplan-Meier product limit estimator will be employed to evaluate rwEFS/rwRFS and rwOS. The time origin for these analyses will be the start of the treatment in the respective line of therapy for rwEFS/rwRFS for the first 3 R/R-based lines of therapy. The time origin of rwOS analysis is the start of the earliest line of Mylotarg therapy. rwEFS/rwRFS and rwOS analyses for lines of therapy will be limited to patients who received treatment during the line of interest.

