rwEFS will be defined as the time from the treatment initiation date (for the first line of Mylotarg-containing therapy) to the date of treatment failure (TF), relapse from CR or better, or death from any cause, whichever comes first. TF is defined as failure to achieve CR or better following up to 3 cycles of Mylotarg. Accordingly, the time origin for rwEFS will be the start of Mylotarg in the first line of therapy in which it is used. The terminal event for analysis of rwEFS is the earlier of treatment failure, relapse from CR or better (as evidenced by provider documentation), or death. Patients who have not died or experienced an event by the date of last contact within the medical record will be censored for analysis of rwEFS.

rwRFS will be defined as the time from the treatment initiation date (during the first line of Mylotarg-containing therapy) to the date of a relapse event, or death from any cause, whichever comes first. The time origin for rwRFS will be the start of Mylotarg in the first line of therapy in which it is used. The terminal event for analysis of rwRFS will be the earlier of a relapse event (as evidenced by provider documentation), or death. Patients who have not died or experienced a relapse event by the date of last contact within the medical record will be censored for analysis of rwRFS.

The time origin of rwOS analysis is the start of the first Mylotarg use. The terminal event for analysis of rwOS is date of death. Note that Social Security Disability Insurance (SSDI) records have an expected lag of up to 4 months. Accordingly, patients who are not indicated to be deceased in clinical records or SSDI records will be censored for rwOS analysis as of the later of 1) the latest date known alive within the clinical record, 2) 4 months prior to the date of most recent SSDI update.

Separate Kaplan-Meier analyses will be conducted for each rwEFS, rwRFS and rwOS endpoint.

#### 4.3.6. Methods under Objective 4

*Objective 4: To evaluate response among AML patients who received Mylotarg in a real-world setting.*

- a. First and best response for each regimen in the first qualifying Mylotarg-containing R/R-based line of therapy.
- b. Time to best response for each regimen in the first qualifying Mylotarg-containing R/R-based line of therapy.
- c. Duration of best response for each regimen in the first qualifying Mylotarg-containing R/R-based line of therapy.

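### The SAP gives rwRFS conflicting event rules (relapse or death in its own definitions, an R/R event in the pooled text), so living refractory patients are classified differently

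*SAP*

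**What the plan says.** **Relapse or death.** The rwRFS paragraph of SAP 4.3.5 reads: "The terminal event for analysis of rwRFS will be the earlier of a relapse event (as evidenced by provider documentation), or death". It then censors at last contact anyone with neither. The rwRFS bullet in SAP 4.3.2 runs from treatment start "in the first line of therapy) to the date of a relapse event, or death from any cause, whichever comes first", and the matching bullet in Protocol 9.7.2 has the same endpoint.

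**R/R event, sometimes with progression.** Four passages treat rwEFS and rwRFS as a pair:
- The last paragraph of SAP 4.3.2 says "the terminal event is the earlier of an R/R event or death". Protocol 9.7.2 closes with the same sentence.
- Protocol 9.7.5 has "the earlier of death or the first date of disease progression or R/R event following the time origin".
- SAP 3.5.2 derives observation time for "rwEFS/rwRFS, by line, based on start date of treatment within line and dates of R/R event or disease progression, or censoring". It is keyed to Tables 5 to 7, and Table 7 is rwRFS. Death is not named.
- Protocol 9.3.4 has nearly the same derived-variable line.

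**Links between the sections.** SAP 4.3.5 says "The outcomes of interest under this objective are rwEFS/rwRFS and rwOS. Time to event analysis as described in" Section 4.3.2 will be used. SAP 4.3.2 in turn opens by deferring to what the objectives specify. SAP 4.1 lists rwRFS among the primary endpoints. Table 7 and Figure 2 report it for all patients from the start of the first Mylotarg-containing line.

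**The concern.** An R/R event covers both relapsed and refractory disease, and SAP 4.2 defines the two separately. Relapse is recurrence or worsening after at least a minimal response. Refractory disease is failure to reach one. A patient who never responds cannot relapse in that line, so the two rules give that patient different outcomes.

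The rwRFS analysis is not limited to responders, so these patients are in the risk set. Two programmers who each follow a visible passage of the same SAP could report different medians and curves for a listed primary endpoint. A reader of Table 7 could not tell which rule had been used.

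**Working it through.** The plan states no rwRFS figure to reproduce. The sample of 20 to 30 is a feasibility count without a power calculation. The check is first textual; an illustration of size follows.

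**Step 1: the passages side by side**

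| Place | rwRFS event |
|---|---|
| SAP 4.3.2, rwRFS bullet | relapse or death |
| SAP 4.3.5, rwRFS paragraph | relapse or death |
| Protocol 9.7.2, rwRFS bullet | relapse or death |
| SAP 4.3.2, closing paragraph (pooled) | R/R event or death |
| Protocol 9.7.2, closing paragraph (pooled) | R/R event or death |
| Protocol 9.7.5 (pooled) | R/R event, progression or death |
| SAP 3.5.2 and Protocol 9.3.4 (pooled) | R/R event or progression; death not named |

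SAP 4.3.2 disagrees with itself, and its closing paragraph disagrees with SAP 4.3.5.

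**Step 2: one patient.** Suppose a patient is documented as refractory at month 2, has no later relapse, and is alive at last contact at month 8. Relapse or death: censored at 8 months. R/R event or death: event at 2 months.

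**Step 3: illustrative size.** None of these event times or shares comes from the documents.
- q is the refractory share.
- Responders respond at 1.5 months and have a median of 12 months from response to relapse or death.
- Refractory patients have median survival of 6 months from treatment start, and no later relapse.
- Refractory status is dated at 3 cycles × 21 days = 63 days = 2.07 months. The 21-day cycle is the SAP 4.2 convention.

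Responder curve: R(t) = 1 up to 1.5 months, then 2^(−(t−1.5)/12).

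Relapse or death: S(t) = (1−q)·R(t) + q·2^(−t/6).

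R/R event or death: the same, with the second term 0 from 2.07 months. Its median is 1.5 + 12·log2((1−q)/0.5).

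- q = 0.10, R/R rule: 1.5 + 12·log2(1.8) = 11.68 months. Relapse rule: 12.51 months, where 0.476 + 0.024 = 0.500. Gap 0.8 months.
- q = 0.20, R/R rule: 1.5 + 12·log2(1.6) = 9.64 months. Relapse rule: 11.56 months, where 0.447 + 0.053 = 0.500. Gap 1.9 months.

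At 6 months R(6) = 2^(−4.5/12) = 0.771. The event-free proportions are:
- q = 0.10: 0.9 × 0.771 = 0.694 under the R/R rule, and 0.694 + 0.1 × 0.5 = 0.744 under the relapse rule.
- q = 0.20: 0.617 and 0.717.

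Patients whose status differs at 6 months number N × q × 0.5. That is 1 to 1.5 of 20 to 30 patients at 10%, and 2 to 3 at 20%.

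**Step 4: sensitivity.** With responder medians of 8 or 12 months and refractory survival medians of 4, 6 or 9 months, the gap is 0.4 to 1.3 months at 10% and 1.1 to 2.9 at 20%. In the base case, medians are 10.7 v 7.3 months at 30% and 9.8 v 4.7 at 40%.

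A separate Kaplan-Meier simulation used other assumptions: refractory at 2 months, median survival 5 months after that, median 12 months to relapse or death in the rest, and follow-up of 6 to 24 months. With 30 patients it gave 11.1 v 10.1 months at 10% and 10.4 v 7.8 at 20%. Direction and scale agree.

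**The case against.** The best defence is that the governing rule can be inferred. SAP 4.3.5 gives rwRFS its own definition, time origin, event and censoring rule, all on relapse or death, and it replaces the pooled sentence of Protocol 9.7.5. SAP 4.3.2 opens by deferring to the objectives. Objective 3a points to the definition in 4.3.2, where the only sentence defining rwRFS alone is relapse or death. The pooled sentence does not fit rwEFS well either, since the rwEFS event includes treatment failure. It looks like leftover shorthand.

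Most of this stands, and it makes relapse or death the more natural reading. It does not remove the conflict: SAP 4.3.5 also invokes 4.3.2, the pooled sentence there names rwRFS, and no visible passage ranks the two. Part of 4.3.2 is redacted, so a ranking may exist out of sight.

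Four stronger readings are tempting and not supported:
- *SAP 3.5.2 yields the R/R-or-death rule.* It omits death, so taken literally it yields neither rule.
- *The protocol passages are equally serious.* Protocol 9.7 lets the SAP modify its plans, and Protocol 9.3.4 leaves formal variable definitions to the SAP. The conflict that matters is inside the SAP.
- *The medians differ by three to five months.* That needs a refractory share of 30 to 40%, which is the complement of the 60 to 70% background complete remission rate. Refractory here means failing even a minimal response, so partial responders are not refractory, and that share is likely an upper end.
- *rwRFS must be restricted to responders.* That would be a different analysis, and the contradiction can be removed without it.

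**Conclusion.** Wrong as written. The current SAP contains incompatible event rules for a listed primary endpoint, and the difference falls on living refractory patients, who are in the Table 7 population. That conclusion rests on the text alone.

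The size cannot be fixed from the documents because they give no refractory share. On the assumptions shown, the effect on the median is modest at 10 to 20% refractory and grows with the share. With 20 to 30 patients the median will be imprecise in any case, which limits the practical effect but does not settle which quantity is being estimated.

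No hypothesis test or decision depends on this, and treatment failure remains visible in rwEFS (Table 6). What is at stake is whether the rwRFS median and curve mean what their definition says.

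**What to change.** 1. State one rwRFS event rule, relapse or death, as the endpoint-specific definitions already do.
2. Remove rwRFS from the pooled sentence that closes SAP 4.3.2.
3. In SAP 3.5.2, give rwRFS its own derived-variable line built from start date, relapse date, death date and last contact.
4. Footnote Table 7 and Figure 2: all patients are included, refractory status is not an rwRFS event, and treatment failure is counted in rwEFS (Table 6).
5. If the protocol is amended, align 9.3.4, 9.7.2 (closing paragraph) and 9.7.5. The change confirms the existing rwRFS definition, so whether Protocol 9.7 calls for an amendment is for the sponsor to judge.

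The cost is two wording edits in the SAP, one footnote text, and up to three matching protocol edits. The rwRFS line does need relapse dates that can be told apart from refractory dates, so check that abstraction records them separately. A supplementary responder-only row is optional and not part of the repair.

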## 2. LIST OF ABBREVIATIONS

Abbreviation	Definition
AE	Adverse event
AEM	Adverse event monitoring
AIDS	Acquired immunodeficiency syndrome
AML	Acute myeloid leukemia
BMI	Body mass index
CR	Complete response
CRF	Case report forms
CRh	Complete response with partial hematologic recovery
Cri	Complete response with incomplete hematologic recovery
CRN	Clinical Research Nurse
DCT	Data collection tools
ECOG	Eastern Cooperative Oncology Group
EFS	Event-free survival
ELN	European LeukemiaNet
EMR	Electronic medical record
FDA	Food and Drug Administration
FISH	Fluorescence in situ Hybridization
FLT3	Fms-like tyrosine kinase 3
GO	gemtuzumab ozogamicin
HIV	Human immunodeficiency virus
HMA	Hypomethylating agent

PFIZER CONFIDENTIAL

Abbreviation	Definition
IDH1/2	Isocitrate dehydrogenase 1/2
IEC	Independent ethics committee
IM	Intramuscular
IRB	Institutional review board
ISPOR	International Society for Pharmacoeconomics and Outcomes Research
IV	Intravenous
MDS	Myelodysplastic syndromes
MLFS	Morphologic leukemia-free state
MPN	Myeloproliferative neoplasms
NE	Not evaluable
NIS	Non-interventional study
NPM1	Nucleophosmin 1
OS	Overall survival
PD	Progressive disease
PR	Partial response
R/R	Relapsed/refractory
RFS	Relapse-free survival
RW	Real world
SAP	Statistical analysis plan
SD	Stable disease
SQL	Structured query language
SSDI	Social Security Death Index

PFIZER CONFIDENTIAL

Abbreviation	Definition
TF	Treatment failure
TP53	Tumor protein 53
US	United States

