### 3.5.1.2. Extracted Data

Data extracted for eligible patients from the structured data that are available in the Definitive Oncology Dataset through SQL query will include the following:

- Insurance status (private only, public only, both, neither) (Table 1).
- State of residence (Table 1).
- Sex (Table 1).
- Height (Table 1).
- Weight at index date ( $\pm 30$  days) (Table 1).
- Date of birth (Table 1).
- Date of death (Table 8).

- Treatments, dates of treatments, dose, and schedule for all oral (if applicable), infused, or injected anti-cancer therapies from the index date through the end of the third R/R-based line of therapy or the end of the record, whichever comes first (Table 3-Table 5).

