A discontinuation will be defined as stopping of a particular agent for any reason, as indicated by provider documentation of “discontinuation” or “change in therapy” in the medical record, or, in the absence of provider documentation of discontinuation or change in treatment, a change in treatment with a particular agent, with no further treatment with that agent documented in structured data, or, evidence that the patient is admitted to hospice care (as the assumption is made that all systemic therapy is discontinued at that time).

For purposes of this study, first line therapy will be defined as beginning with the first regimen the patient receives after diagnosis of the disease of interest. Subsequent lines in this study will be defined as *R/R-based lines*. *R/R-based lines* are defined by the occurrence of an R/R event or a disease progression - either may be cited, in which an R/R event or disease progression must occur for a new regimen to be interpreted as a new line of therapy. In this study, **refractory** AML is defined as disease that is nonresponsive or failing to achieve at least minimal response while on therapy. **Relapsed** status is defined as the recurrence or worsening of disease following achievement of at least a minimal response. Additionally, the documentation of advancement of disease in patients after initial AML diagnosis but before initial AML treatment will be interpreted as a disease progression. R/R events and disease progression will be defined based on provider documentation, which primarily includes progress notes.

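### Date of death and last date known alive are not on the nurse-curated lists, yet the rwOS censoring rule carries any patient without a recorded death to at least 4 months before the SSDI update

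*SAP*

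**What the plan says.** **Endpoint.** SAP 4.1 names rwOS among the primary endpoints. Death is also a component of rwEFS and rwRFS.

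**Where death is collected.** Date of death is listed in Protocol 9.3.3 and SAP 3.5.1.2. SAP 3.5.1.2 describes its contents as "Data extracted for eligible patients from the structured data that are available in the Definitive Oncology Dataset through SQL query". It links date of death to Table 8 (rwOS) only. The nurse-curated lists in Protocol 9.3.2 and SAP 3.5.1.1 go down to individual translocations but include neither date of death nor last date known alive.

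**How death is used.** Under SAP 4.3.5, "patients who are not indicated to be deceased in clinical records or SSDI records will be censored for rwOS analysis", and the censoring date is the "later of 1) the latest date known alive within the clinical record, 2) 4 months prior to the date of most recent SSDI update". Protocol 9.7.5 has the same rule. The only reason given for the 4 months is reporting lag.

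**Other wording.** SAP 4.3.2 runs rwOS to the end of the record or death and adds: "Patients who are not indicated to be deceased at last known contact (patients who are alive, or lost to follow-up) will be censored". Protocol 9.7.5 and SAP 4.3.5 expand the source differently from the abbreviation list. The methods text reads "Note that Social Security Disability Insurance (SSDI) records have an expected lag of up to 4 months", while Protocol Section 2 has "Social Security Death Index". The data-source sections (Protocol 9.4, SAP 3.2) describe no linkage to either file.

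**The concern.** The rwOS rule needs two facts from the chart: whether the patient is recorded as dead, and when the patient was last known alive. Neither is a planned abstraction item, although nurses read every chart. SAP 4.2 already uses "evidence that the patient is admitted to hospice care" from the record as a sign that treatment has stopped.

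The later-of rule puts a floor under the censoring date. A patient whose death is missed by both sources is not censored when last seen. The patient stays in the risk set, event-free, until at least 4 months before the SSDI update. This error can only raise rwOS. With 20-30 patients, a few such cases would move the curve, and the planned outputs would not show how many there were.

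**Working it through.** The plan states no expected rwOS, event count or capture rate, so there is no figure to reproduce. The check sets needs against planned collection and then sizes the effect under assumptions.

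**1. Needed versus listed**

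| Item used in SAP 4.3.5 | Structured list | Nurse-curated list |
|---|---|---|
| Date of death | yes | no |
| Last date known alive in the record | no | no |
| SSDI record and update date | no | no |

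**2. Length of the carry-forward.** Floor = SSDI update minus 4 months minus Mylotarg start. The update date is not stated. I assume April 2020, the planned end of data collection in Protocol 6; a later update lengthens the floor. SAP 3.4.1 sets 1 September 2017 as the earliest Mylotarg date.
- Start September 2017: 31 - 4 = 27 months.
- Start September 2019: 7 - 4 = 3 months.
- Example: start October 2017, last contact January 2018, death soon after and missed by both sources. The patient is censored in December 2019, at about 26 months instead of about 3.

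**3. Effect of one missed death.** When all patients are followed past the time in question, each missed death raises the survival proportion by 1/30 = 3.3 to 1/20 = 5.0 percentage points.

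**4. Effect on the curve.** Let f be the share of deaths missed by both sources and S(t) true survival. If everyone is followed to the floor, the Kaplan-Meier curve estimates

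S_rep(t) = f + (1 - f) S(t).

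For exponential survival with true median M, the reported median is M × log2[(1 - f)/(0.5 - f)]. I take M = 12 months.

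The simulations (one million patients, exponential survival) spread starts evenly over 31 months, run the record to month 31 and the index to month 27. The last two columns add exponential loss to practice follow-up with mean 20 months. All of these are assumptions.

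| Deaths missed | (1-f)/(0.5-f) | Formula median | Later-of, no loss | Later-of, with loss | Censor at last date alive, with loss |
|---|---|---|---|---|---|
| 0% | 2.000 | 12.0 | 12.0 | 12.0 | 10.6 |
| 5% | 2.111 | 12.9 | 12.9 | 12.9 | 11.0 |
| 10% | 2.250 | 14.0 | 13.9 | 14.0 | 11.5 |
| 20% | 2.667 | 17.0 | 16.5 | 16.7 | 12.6 |
| 30% | 3.500 | 21.7 | 20.3 | 20.9 | 13.8 |

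The simulated later-of medians fall slightly below the formula because deaths missed in the final 4 months are not carried forward.

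Twelve-month survival by the formula is f + (1 - f) × 0.5: 50% true, and 52.5, 55, 60 and 65% for f = 5, 10, 20 and 30%.

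**5. Other true medians.** The multiplier does not depend on M. At f = 20% it is log2(2.667) = 1.415, so 6 months becomes 8.5 and 10 becomes 14.2.

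**The case against.** **The notes may already count.** A reader might infer that a death written only in a progress note is ignored. The documents do not support that. The rule takes death from clinical records or SSDI, and Protocol 9.4 says the dataset includes physician notes and a nearly complete oncology record. SAP 4.4 adds that some outcomes missing from structured fields can be abstracted. This stands: a death must be missed by both sources, and a note-only death is lost only if the curated list is followed literally. What remains is a gap in specification, because no planned field records a death found by the nurse.

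**The later-of rule has a purpose.** A reader might also infer that the rule is wrong and that last-contact censoring should replace it. That does not follow. With loss to follow-up, the death file supplies deaths after last contact. Stopping survivors' time at last contact while counting those deaths biases rwOS low: 10.6 against a true 12 months at complete capture, when the later-of rule gives 12.0. In the same set-up the two rules err about equally at 5% missed, and last-contact censoring is closer from 10% up. The choice turns on a capture rate the documents do not give.

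**rwEFS and rwRFS are not carried forward.** SAP 4.3.5 censors both at last contact. A different rule is defensible, since relapse is seen only in the record. A missed death still removes an event from them.

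**SAP 4.3.2 does not set a rival censoring date.** Its sentence says who is censored; 4.3.5 gives the date. The loose part is the phrase that ends rwOS follow-up at the end of the record.

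**Sampling error is larger.** At n = 25, true median 12 and perfect capture, simulated Kaplan-Meier medians ran from about 6 to 29 months (central 95%). True, but the interval does not reflect a one-directional error.

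**Conclusion.** The concern holds as a gap in data specification for a primary endpoint, with a conditional upward bias in rwOS. The later-of rule relies on complete death capture, while the chart facts that would support it are not planned data elements. The death source also has two names and no stated linkage or completeness.

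The size depends on the assumed capture rate. For a true median of 12 months, the bias is nil at complete capture, about 1 month at 5% missed, 2 at 10%, 4.5 at 20% and 8 at 30%. These figures rest on exponential survival, even accrual and an April 2020 SSDI update. Long false survival arises mainly in patients who started Mylotarg early. The documents do not show that deaths will be missed, and they do not justify dropping the later-of rule.

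**What to change.** 1. Add date of death, source of death and last date known alive to the nurse-curated lists (Protocol 9.3.2, SAP 3.5.1.1). State that death for rwOS, rwEFS and rwRFS uses all sources, and link the field to Tables 6 to 8.
2. Keep the later-of rule as the primary rwOS censoring rule. Add a sensitivity Kaplan-Meier analysis that censors at last date known alive, and report how many patients the primary rule censors beyond their last contact.
3. Reconcile the end of rwOS follow-up in SAP 4.3.2 with 4.3.5. Name the death source consistently (Death Index or Disability Insurance), and state its linkage, update date and any known completeness.

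Cost: two extra abstraction fields (death date with its source, and last date known alive) on 20-30 charts that nurses already read, one extra analysis and some wording. The reported median rwOS may come out shorter.
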